5.1.2. Placebo Investigational Medicinal Product

The placebo will be the same vehicle and excipients as those for fremanezumab. See [Table 6](#) for additional details.

5.2. Preparation, Handling, Labeling, Storage, and Accountability for Investigational Medicinal Products

Information pertaining to the preparation, handling, labeling, storage, and accountability for the IMP used in this study can be found in [Appendix G](#).

5.3. Justification for Investigational Medicinal Products

5.3.1. Justification for Dose of Test Investigational Medicinal Product

[figure not shown]
As noted in Section [5.1.1.1](#), as of June 15 2015, CCH patients are no longer enrolling in this study.

Patients who received fremanezumab at 225 mg sc monthly after a loading dose of 900-mg iv or 675 mg sc or fremanezumab at 675 mg sc quarterly during the pivotal studies will continue receiving the same dose (ie, 225 mg sc monthly or 675 mg sc quarterly depending upon their diagnosis and randomization in the pivotal studies) during this long-term safety extension study. These dose regimens are expected to maintain steady state at a blood concentration level that will provide clinical efficacy. The doses and dosing regimens also account for the usual course of the 2 forms of CH; patients with ECH are likely to remit after initial treatment whereas CCH patients are continuously inflicted by pain.

Patients who received placebo during the pivotal studies will be assigned to receive either fremanezumab 675 mg sc quarterly (patients with ECH from Study TV48125-CNS-30056) or a loading dose 675 mg sc followed by monthly fremanezumab at 225 mg sc monthly (patients with CCH from Study TV48125-CNS-30057). This will provide these patients with the opportunity to receive potential benefit from therapeutic doses including the loading dose of 675 mg sc.

In addition to evaluating maintenance of efficacy in this long-term safety extension study, the planned treatments account for the need to adjust treatment duration, which is of particular relevance for ECH. When the cluster cycle is almost over in ECH, the number of headache attacks per day start to decrease with associated mild to moderate intensity. Patients often look for preventive options in the very early part of the headache cycle in an attempt to reduce its duration. Equally, when complete remission is achieved, patients with ECH consider stopping

their medication and thus withdraw from treatment when the cluster period is over ([May 2005](#)). Accordingly, continuous long-term treatment in ECH might not be needed as these patients may have long remission periods between the cluster episodes.

5.4. Restrictions

Patients will be required to comply with the following restrictions:

5.4.1. Activity

Patients must remain at the investigational center for safety observation for at least 60 minutes after IMP administration. Patients may be asked to remain at the investigational center longer if it is judged to be medically necessary.

5.4.2. Blood Donation

Patients may not donate blood while taking the IMP and for 5 half-lives (7.5 months) after the last dose of the IMP.

5.4.3. Pregnancy

Restrictions in regard to pregnancy are provided in the inclusion criteria (Section [4.1](#)). Restrictions in regard to sexual activity are also detailed in the inclusion and exclusion criteria (Section [4.1](#)), and contraception methods are reviewed in [Appendix E](#).

In addition, male patients may not donate sperm for the duration of the study and for 7.5 months (approximately 5 half-lives of the active IMP) after administration of the last dose of the IMP.

5.5. Prior and Concomitant Medication or Therapy

Any concomitant medication, treatment, or procedure from the time of consent up to the end of the study, including follow-up, will be recorded on the CRF. Trade name and International Nonproprietary Names (if available), indication, dose, and start and end dates of the administered

medication will be recorded. The sponsor will encode all medication and treatment according to the World Health Organization drug dictionary.

Patients taking concomitant preventive medications (ie, verapamil, topiramate, valproate, lithium, or methysergide) during the pivotal studies must begin tapering as soon as they begin participation in this study, and they must be off these medications within 1 month from the beginning of participation in this study (not applicable for patients participating in safety follow-up only). See [Appendix H](#) for details.

For daily prescribed medications, patients must be on a stable dose and regimen for at least 2 weeks prior to screening and throughout the study.

All concomitant medications taken during the study must be recorded with indication, daily dose, and start and stop dates of administration. All patients will be questioned about concomitant medication at each visit.

5.6. Procedures for Monitoring Patient Compliance

The investigator will be responsible for monitoring patient compliance. A check of compliance with IMP intake will be performed during each visit after the IMP has been administered, and IMP accountability records will be completed.

If the investigator or the sponsor determines that the patient is not in compliance with the study protocol, the investigator and the sponsor should determine whether the patient should be withdrawn from the study.

Exposure to IMP will be assessed as required.

5.7. Temporary Discontinuation of Investigational Medicinal Product

Patients who experience CH remission, defined as no CH attacks for 12 successive weeks and 24 successive weeks for patients with ECH and CCH, respectively, at any time after starting IMP (ie, administration of the first dose of IMP in the pivotal study) will be offered the possibility to stop treatment. Patients will restart fremanezumab treatment if treatment is stopped and CH attacks resume during the 36-week double blind treatment period. Refer to Section 5.1.1.1 for additional details regarding treatment of these patients. After 15 June 2018, only patients who participated in the ECH study (Study TV48125-CNS-30056) will be enrolled for active treatment.

5.8. Randomization and Blinding

This is a double-blind study; blinding will be retained from the pivotal studies and throughout this long-term safety extension study. Patients will be assigned to treatments as described in [Table 3](#) and Section 5.1.1.1 based on their randomization in the pivotal studies (Studies TV48125-CNS-30056 and TV48125-CNS-30057).

5.9. Maintenance of Randomization and Blinding

5.9.1. Maintenance of Randomization

Refer to the protocols for the pivotal studies (Studies TV48125-CNS-30056 and TV48125-CNS-30057) for details regarding randomization of patients in this study.

Packaging vendor(s) will package test IMP and placebo IMP into single-visit kits according to Good Manufacturing Practice (GMP) procedures. Kits will be identical in appearance. Adequate kit supply for upcoming study visits will be managed by interactive response technology (IRT) and kept (refrigerated at 2°C to 8°C) at the investigational centers.

At visits 1 through 10, the IRT will be queried, and investigational center personnel will retrieve and administer each prefilled syringe contained in the appropriately numbered kit(s). Kit numbers will be entered into the CRF.

5.9.2. Blinding and Unblinding

Blinding will be retained from the pivotal studies and throughout this long-term safety extension study.

Blinded pharmacokinetics data may be assessed during the study. Personnel responsible for bioanalysis (pharmacokinetics and immunogenicity) will be provided with the randomization code to facilitate the analysis. However, the personnel responsible for bioanalysis and pharmacokinetics data analysis will not have access to clinical safety and efficacy data and will provide concentration data to other personnel in a manner that will not identify individual patients (ie, a dummy patient identifier will be linked to the concentration data of an individual patient).

For information about personnel who may be aware of IMP assignments, see Section 5.8 of the pivotal efficacy protocols. These individuals will not be involved in conduct of any study procedures or assessment of any adverse events.

In the event of an emergency, it will be possible to determine which treatment group and dose the patient has been allocated to by accessing the Randomization and Trial Supply Management (RTSM) system. All investigational centers will be provided with details of who can access the system for code breaking at the start of the study. The Medical Monitor or equivalent should be notified following unblinding. Any unblinding of the IMP performed by the investigator must be recorded in the source documents.

In case of a serious adverse event, pregnancy, or in cases when knowledge of the IMP assignment is needed to make treatment decisions, the investigator may unblind the patient's IMP assignment as deemed necessary, mainly in emergency situations, through specialized access in the RTSM system. Breaking of the treatment code can always be performed by the investigator without prior approval of the sponsor; however, the sponsor should be notified that the code was broken, but the patient's IMP assignment should not be revealed to the sponsor. In the event that the RTSM system is not functioning for emergency unblinding, the next course of action is to contact via phone the RTSM on-call customer support helpline for manual emergency unblinding.

When a blind is broken, the patient will be withdrawn from the study and the event will be recorded onto the CRF. The circumstances leading to the breaking of the code should be fully documented in the investigator's study files and in the patient's source documentation. Treatment assignment should not be recorded in any study documents or source document.

In blinded studies, for an adverse event defined as a suspected unexpected serious adverse reaction (SUSAR) (ie, reasonable possibility; see Section 7.1.4), Global Patient Safety and Pharmacovigilance may independently request that the treatment code be broken (on a case-by-case basis) to comply with regulatory requirements. The report will be provided in an unblinded manner for regulatory submission. If this occurs, blinding will be maintained for the investigator and for other personnel involved in the conduct of the study, and analysis and reporting of the data.

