4.3. Withdrawal Criteria and Procedures for the Patient

Each patient is free to withdraw from this study at any time, without prejudice to their continued care. Patients must be withdrawn from this study if any of the following events occur:

1. Patient withdraws consent or requests discontinuation from this study for any reason.
2. Patient develops an illness that would interfere with his/her continued participation.

3. Patient is noncompliant with the study procedures and assessments or administration of IMPs (including noncompliance with wearable sensor substudy, if applicable) in the opinion of the investigator.
4. Patient takes prohibited concomitant medications as defined in this protocol.
5. A female patient has a confirmation of pregnancy during the study from a positive pregnancy test result.
6. The sponsor requests withdrawal of the patient.
7. Patient experiences an adverse event or other medical condition which indicates to the investigator that continued participation is not in the best interest of the patient.
8. The investigator and/or sponsor may withdraw an individual patient from the study at any time for any reason (eg, lack of efficacy, protocol deviation as defined in Section 10, noncompliance, or adverse event). In addition, patients with positive eC-SSRS findings or abnormal hepatic laboratory values (eg, ALT, AST, ALP, GGT, bilirubin [total, direct, or indirect], or INR) may meet criteria for discontinuation from the IMP as summarized in [Appendix J](#).

In the event that a patient was incorrectly enrolled and has already started taking the study drug, a risk/benefit evaluation should take place between the investigator and sponsor, and a strong clinical justification must be provided if the patient is not withdrawn from study drug.

Patients should be treated with standard of care after withdrawal from or termination of the study as appropriate.

Investigators should attempt to obtain information on patients in the case of withdrawal or discontinuation. Results of any evaluations and observations, together with a narrative describing the reason(s) for withdrawal, must be recorded in the source documents. The case report form (CRF) must document the primary reason for withdrawal or discontinuation.

See [Appendix F](#) for information regarding how the study will define and address lost to follow-up patients to help limit the amount and impact of missing data.

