- Obtain a 17-mL blood sample for biomarker analysis (8.5 mL for serum, 6 mL for plasma, and 2.5 mL for RNA).
- Complete the eC-SSRS Since Last Visit version.
- Administer the HADS, EQ-5D questionnaire, SF-12 questionnaire, and WPAI questionnaire.
- Complete the PPSI.
- Complete the PGIC scale.
- Each patient's partner/family member completes the Impact on Partner and Family questionnaire. Partners/family members will be asked to attend the study visit with the patient or to return to the investigational center within ± 3 days of the patient's visit if unable to appear at the same time.
- Perform wearable sensor device check and compliance check for patients enrolled in the wearable sensor substudy.

After completing predose assessments, patients who are not in CH remission will be treated with IMP. Refer to Section 5.1.1.1 for details.

The following procedures/assessments will be performed after dosing:

- Perform local injection site assessment immediately (+10 minutes) and at 1 hour (± 15 minutes) after completing IMP administration. Additional injection site assessments may be performed based on the severity of any observed injection site reaction. See Section 7.11 for additional details.
- Evaluate for anaphylaxis and hypersensitivity reactions.
- Inquire about postdose adverse events before the patient leaves the investigational center.

Additional Visit(s) for Patients in the Wearable Sensor Substudy

End-of-Treatment Visit (Visit 11 [Week 40 \pm 3 Days])/Early Withdrawal Visit

The following procedures/assessments will be performed at the EOT/early withdrawal visit:

- Review electronic diary data.
- Review study compliance.
- Perform vital signs measurements (includes systolic and diastolic blood pressure, pulse, and body temperature).
- Perform triplicate 12-lead ECGs.
- Perform a physical examination (including weight).
- Inquire about adverse events.
- Inquire about concomitant medications.
- Perform clinical laboratory tests (serum chemistry, hematology, coagulation, and urinalysis).
- Perform a serum β -HCG test (WOCBP only).
- Obtain a 4-mL blood sample for pharmacokinetics analysis.
- Obtain a 5-mL blood sample for ADA analysis.
- Obtain a 5-mL urine sample for biomarker analysis.
- Obtain a 17-mL blood sample (8.5 mL for serum, 6 mL for plasma, and 2.5 mL for RNA) for biomarker analysis.

- Complete the eC-SSRS Since Last Visit version.
- Administer the HADS, EQ-5D questionnaire, SF-12 questionnaire, and WPAI questionnaire.

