- Complete the PPSI and the PGIC scale.
- Collect the electronic diary device.
- Each patient's partner/family member completes the Impact on Partner and Family questionnaire. Partners/family members will be asked to attend the study visit with the patient or to return to the investigational center within ± 3 days of the patient's visit if unable to appear at the same time.
- Perform wearable sensor device check and compliance check for patients enrolled in the wearable sensor substudy.
- Collect wearable sensor device from patients enrolled in the wearable sensor substudy.

3. Procedures after IMP Treatment

Follow-up Visit (Visit 12 [Week 68 \pm 1 Week])

Patients who participate in the study in compliance with the protocol for the entire treatment period (ie, from visit 1 through visit 11) will be considered to have completed the study. Patients may be treated with standard of care following completion of visit 11. See Section 3.1 for the definition of the end of study.

Patients who complete the double-blind treatment period will have a follow-up visit approximately 7.5 months (5 half-lives) after the final dose of IMP. The following procedures/assessments will be performed at this visit:

- Perform vital signs measurements (includes systolic and diastolic blood pressure, pulse, and body temperature).
- Perform physical examination (including weight).
- Inquire about adverse events.
- Inquire about concomitant medications.
- Complete the eC-SSRS Since Last Visit version.
- Obtain a 5-mL blood sample for ADA analysis.
- Obtain a 5-mL urine sample for biomarker analysis.
- Obtain a 17-mL blood sample (8.5 mL for serum, 6 mL for plasma, and 2.5 mL for RNA) for biomarker analysis.

Patients who discontinue treatment prematurely must be encouraged to continue to attend the regular scheduled visits, and complete the prescribed safety and efficacy evaluations through the EOT visit (visit 11 [week 36]) and the follow-up visit (visit 12 [week 40]), if at all possible.

Patients who both discontinue treatment and also withdraw from the study should have EOT (early withdrawal) visit procedures/assessments (see [Table 4](#)) performed on the last day the patient receives the IMP, or as soon as possible thereafter. The patient should also return for the follow-up visit approximately 7.5 months after the last dose of IMP if at all possible.

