Procedures for patients who withdraw prematurely from the study are described in [Section 4.3](#). Patients should be treated with standard of care after termination of the study as appropriate.

Patients with ongoing adverse events or clinically significant abnormal laboratory test results (as interpreted by the investigator) will be monitored as described in [Section 7.1.2](#).

4. **Unscheduled Visits**

An unscheduled visit may be performed at any time during the study, at the patient's request or as deemed necessary by the investigator. The date and reason for the unscheduled visit will be recorded on the case report form as well as any other data obtained (eg, adverse events, concomitant medications and treatments, and results from procedures or tests).

Procedures performed during unscheduled visits include the following:

- Review electronic diary data (if applicable).
- Review study compliance.
- Perform vital signs measurements (including systolic and diastolic blood pressure, pulse, and body temperature).
- Inquire about adverse events.
- Inquire about concomitant medications.
- Complete the eC-SSRS Since Last Visit version.

Other procedures may be performed at the discretion of the investigator.

Patients Enrolling in This Study for Evaluation of Antidrug Antibodies and Safety (Adverse Events and Concomitant Medications)

1. **Visit 1**

The following procedures/assessments will be performed at visit 1 for patients who enroll in this study for the purpose of evaluating ADAs, and safety (adverse events and concomitant medications):

- Obtain written informed consent before any other study-related procedures are performed.
- Inquire about adverse events.
- Inquire about concomitant medications.

2. **Follow-up Visit (Visit 12 – Approximately 7.5 months after the last dose of IMP during the pivotal efficacy study)**

Patients enrolling in this study for the purpose of evaluating ADAs and safety (adverse events and concomitant medications) only will attend a visit approximately 7.5 months after receiving the last dose of IMP (during the pivotal efficacy studies). The following procedures/assessments will be performed at this visit:

- Inquire about adverse events.
- Inquire about concomitant medications.
- Obtain a 5-mL blood sample for ADA analysis.

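### A code break by the investigator takes the patient out of the study, not only off IMP, and so ends the remaining 4-weekly safety visits

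*Protocol*

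**What the plan says.** Protocol Section 5.9.2 gives the grounds on which an investigator may open the code: "In case of a serious adverse event, pregnancy, or in cases when knowledge of the IMP assignment is needed to make treatment decisions". No prior sponsor approval is needed, and the "IMP assignment should not be revealed to the sponsor". The consequence has no exception: "When a blind is broken, the patient will be withdrawn from the study and the event will be recorded onto the CRF".

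Section 4.3 lists eight withdrawal items, and a code break is not one of them. Item 5 covers pregnancy. Item 7 covers an adverse event where the investigator judges that "continued participation is not in the best interest of the patient". Item 6 covers a request from the sponsor, and item 8 allows withdrawal at discretion for any reason.

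Appendix B (Procedures after IMP Treatment) has two tracks:

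- **Stops IMP only:** "Patients who discontinue treatment prematurely must be encouraged to continue to attend the regular scheduled visits", with the safety and efficacy evaluations, where possible.
- **Stops IMP and withdraws from the study:** one exit visit with the end-of-treatment procedures, and then "The patient should also return for the follow-up visit approximately 7.5 months after the last dose of IMP if at all possible".

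**The concern.** The primary objective is long-term safety, and Section 5.9.3 provides no Data Monitoring Committee. Section 1.3.1 names liver enzyme elevations and cardiovascular effects among the potential risks, and these are what the scheduled laboratory tests, ECGs and vital signs are there to detect. Because Section 5.9.2 says study and not IMP, a patient unblinded for a serious event can lose those assessments only because the code was opened, even where the investigator would otherwise have kept the patient under observation.

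Removing unblinded patients can protect a randomized comparison, but there is little here to protect. All treated patients receive fremanezumab (Protocol Section 3.3), and SAP Section 7 plans no inferential analysis. Withdrawal also does not undo the disclosure to the site.

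**Working it through.** The plan gives no figure on this point, so the check is a reading of the text followed by a count of visits.

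**Who is affected.** Section 4.3 already withdraws pregnant patients (item 5) and patients whose adverse event makes continuing unwise (item 7). The code-break sentence changes the outcome only for unblinded patients outside these items for whom neither the sponsor (item 6) nor the investigator (item 8) would choose withdrawal.

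**Inputs** (Protocol Table 4; SAP Sections 8.8 to 8.11):

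- Treatment-period visits: 1 to 11, every 4 weeks, weeks 0 to 40.
- Vital signs and eC-SSRS: visits 2 to 12.
- Laboratory tests and triplicate ECG: visits 4, 7, 10 and 11.
- ADA: visits 4, 7, 10, 11 and 12.
- Physical examination: visits 2, 4, 5, 7, 8, 10, 11 and 12.
- The exit visit carries the full visit 11 set of safety assessments. Visit 12 has no laboratory tests or ECG.

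**Formula.** For a break after dosing at visit k, visits k + 1 to 11 remain, which is 11 - k. The exit visit stands in for one of them, so the most that can be lost is (11 - k) - 1 = 10 - k. Each assessment is counted the same way, as those left through visit 11 minus the one done at exit. Visit 12 is kept in both tracks.

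| Break after visit | Visits (with vital signs and eC-SSRS) lost | Laboratory/ECG/ADA sets lost | Physical examinations lost |
|---|---|---|---|
| 1 | 10 - 1 = 9 | 4 - 1 = 3 | 7 - 1 = 6 |
| 4 | 10 - 4 = 6 | 3 - 1 = 2 | 5 - 1 = 4 |
| 7 | 10 - 7 = 3 | 2 - 1 = 1 | 3 - 1 = 2 |
| 10 | 10 - 10 = 0 | 1 - 1 = 0 | 1 - 1 = 0 |

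**Does another track restore the visits?** Section 3.1 offers safety and ADA follow-up without dosing. Its schedule (Table 5) has only visits 1 and 12, plus unscheduled visits for a safety concern, so it does not.

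**What the analysis keeps.** SAP Section 4.4 drops early withdrawal data from the by-visit summaries but keeps them in Last Assessment. They also enter the summaries of potentially clinically significant laboratory and vital-sign values (SAP Sections 4.1, 8.8 and 8.10), and the worst-value ECG shift covers all of a patient's recorded findings (SAP Section 8.11). The loss is therefore the scheduled assessments between exit and the late follow-up visit, and not the exit data.

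**Timing of the late visit.** Visit 12 at week 68 follows a last dose at week 36, so the lag is 68 - 36 = 32 weeks. A last dose at week 0 puts the follow-up near week 32, and one at week 4 puts it near week 36. Both fall before visit 11 at week 40, so revised wording must allow for this. Two inconsistencies in the Protocol matter here. Section 3.1 gives withdrawn patients 7.5 weeks where the synopsis and Appendix B give 7.5 months. The Appendix B sentence on premature discontinuation labels visits 11 and 12 as weeks 36 and 40, against weeks 40 and 68 in Table 4.

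**The case against.** The strongest reply is that this is a design choice that affects almost nobody. Section 5.9.2 describes unblinding as mainly for emergencies. Many patients with such an event would be withdrawn under Section 4.3 anyway. CCH patients were asked to stop treatment from 15 June 2018, and SAP Section 2.1 reports completion in Q2/2019. All of this stands, and the documents give no number of code breaks.

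It can also be said that most safety information survives. The exit visit is full ("The following procedures/assessments will be performed at the EOT/early withdrawal visit" introduces the same list as for end of treatment). Section 7.1.2 follows each adverse event until it resolves or stabilizes. Appendix B keeps monitoring "Patients with ongoing adverse events or clinically significant abnormal laboratory test results". This also stands. What is lost is routine scheduled surveillance after the drug is stopped.

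Third, the comparison is with visits that are only encouraged, where possible. That is correct, and it is why the counts are ceilings. Attendance after stopping IMP is not given, so no expected loss can be computed.

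Finally, the existing rule keeps assessments by unblinded site staff out of safety summaries that are presented by treatment group (SAP Section 8.1). That is a real cost of changing it, but a small one in a descriptive study with few such patients.

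**Conclusion.** The point holds as a cheap improvement to a design choice. An investigator code break forces study withdrawal that no specific Section 4.3 criterion calls for, and it costs an affected patient at most 10 - k scheduled visits. This assumes that the patient would otherwise have attended every visit, that the exit visit takes the place of one of them, and that the late visit is at 7.5 months and not 7.5 weeks.

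A reader might infer more, in four ways that the documents do not support:

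- **That safety follow-up ends at the code break.** It does not: the exit visit, the late visit and the monitoring of open events all remain.
- **That Sections 5.9.2 and 4.3 contradict each other.** Items 6 and 8 leave room for the rule, so the gap is the absence of a specific criterion.
- **That every serious adverse event leads to withdrawal.** Unblinding is permitted for such an event, not required. Where the sponsor breaks the code for regulatory reporting, the investigator stays blinded and Section 5.9.2 treats this as a separate route.
- **That the safety analysis is invalid.** Nothing in the SAP fails because of this rule.

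**What to change.** Replace the sentence in Section 5.9.2 with wording such as:

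> When the investigator breaks the blind, IMP is discontinued and the event is recorded on the CRF; unless a Section 4.3 criterion requires withdrawal from the study, the patient is encouraged to continue the scheduled safety assessments and ADA sampling through visit 11 (week 40), with the follow-up visit about 7.5 months after the last dose of IMP (or at visit 11 if that is later).

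Flag the code break, not the assignment, in the safety listings, so that the assignment is still kept from the sponsor. While the text is open, correct the 7.5 weeks in Section 3.1 and the visit weeks in Appendix B.

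The cost is one protocol sentence, a listing flag and the extra visits for a few patients, on a track that the Protocol already has. The downside is that later event assessments in these patients are made with the regimen known to the site, and the flag lets a reader of the listings identify them.
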